Glaucoma drainage devices are helpful in the management of intractable glaucoma, which does not respond well to conventional medical and surgical therapies. The Ahmed Glaucoma Valve is a glaucoma drainage device that has a flow-resistive valve mechanism.¹⁻³ This valve is helpful in minimizing postoperative hypotony and complications associated with hypotony, including flat anterior chamber, choroidal effusions, and suprachoroidal hemorrhage.^{4,5}

After Ahmed Glaucoma Valve implantation, patients may require adjunctive anti-glaucoma medications for adequate control of intraocular pressure.^{4,6} With smaller glaucoma valve implants, such as the Molteno implant, increasing the device surface area may lead to lower mean intraocular pressure and fewer adjunctive glaucoma medications.^{7,8} However, additional surface area does not dramatically improve the results with larger implants, such as the Ahmed Valve and the Baerveldt implant.⁹⁻¹² In contrast with trabeculectomy, use of adjunctive mitomycin C does not appear to improve the results with the Ahmed Glaucoma Valve.¹³

In experimental studies, different glaucoma drainage implant plate materials may influence capsule formation and influence the results of glaucoma drainage implants.^{14,15} In clinical comparisons, different plate materials have been associated with significant difference of mean postoperative intraocular pressure in some¹⁶⁻¹⁸ but not in all studies.^{19,20} In a randomized prospective trial, transient elevation of intraocular pressure during the early postoperative period,

known as a "hypertensive phase," was less frequent after silicone plate compared with polypropylene plate Ahmed Glaucoma Valve implantation.¹⁶ In addition to implant plate size and material, other variables influencing success of glaucoma drainage implant surgery have been identified, including race, treatment with silicone oil endotamponade, and neovascular glaucoma.²¹

A silicone plate Ahmed Glaucoma Valve has demonstrated efficacy and safety in clinical studies.¹⁶⁻²⁰ An Ahmed Glaucoma Valve plate constructed with porous material, which is Food and Drug Administration (FDA) approved, but has not been studied in clinical trials, may offer advantages in reducing encapsulation of the implant, thereby potentially improving postoperative intraocular pressure control.

2. Device Description

Glaucoma drainage implants used in this study are the Ahmed Glaucoma Valve (New World Medical, Inc., Rancho Cucamonga, CA) Model FP7 (silicone plate, 184 mm² surface area) and Model M4 (porous polyethylene plate, 191 mm² surface area). Both the Model FP7 and Model M4 are Food and Drug Administration-approved for implantation in humans with intractable glaucoma. Both of these valves will be supplied free of charge by New World Medical Inc for use in this study. Each participating site will be responsible for obtaining FP7 and M4 valves from New World Medical. The valves will not be shipped to UVA and then distributed to participating sites.

The Model M4 plate is approximately the same size as the Model FP7 plate (191 mm² and 184 mm² surface area, respectively). However, the theoretical surface area of the M4 is much higher because of the porous nature of the material. The porous polyethylene material is formed by a proprietary process (Porex Corporation, Fairburn, GA). The porous plate material is high density polyethylene with a long history of use in surgical implants (MEDPOR Biomaterial implants). Average pore sizes are greater than 100 micro-meters and pore

volume is in the 50 percent range, with an interconnecting open pore structure that allows for tissue ingrowth.

3. Study Objective

To evaluate and compare the clinical outcomes after implantation of the porous plate (polyethylene) Ahmed Glaucoma Valve with the silicone plate Ahmed Glaucoma Valve in subjects with intractable glaucoma.

4. Study Hypothesis

Eyes undergoing implantation with the porous plate Ahmed Glaucoma Valve are less likely to develop an elevation of intraocular pressure during the post-operative period and subsequently will have lower intraocular pressure and possibly require fewer glaucoma medications as compared with the silicone plate Ahmed Glaucoma Valve.

5. Study Endpoints

All study endpoints refer to the selected study eye only and are measured from Baseline to 12 months post-operative in the porous plate Ahmed Glaucoma Valve group as compared to the silicone plate Ahmed Glaucoma Valve group.

5.1 Primary Endpoint

The primary endpoint is the mean intraocular pressure in the porous plate group as compared to the silicone plate group at 12 months.

5.2 Secondary Endpoints

- (a) The mean number of anti-glaucoma medications in the porous plate group as compared to the silicone plate group at 12 months.
- (b) Surgical success in the porous plate group as compared to the silicone plate group at 12 months. Surgical success is defined as:

Unqualified surgical success: 5 mmHg < intraocular pressure < 22 mmHg with no loss of light perception and no additional glaucoma procedures or glaucoma medications.

Qualified surgical success: 5 mmHg < intraocular pressure < 22 mmHg with no loss of light perception and no additional glaucoma procedures, but with the adjunctive use of glaucoma medications.

6. Study Synopsis

Title:	Comparison of Silicone and Porous Plate Ahmed Glaucoma Valves
Study Period:	12 months, 9 visits: Screening/Baseline; Day of Surgery; Post-Operative Days 1 and 7; and Post-Operative Months 1, 3, 6, 9, and 12. Unscheduled visits will be performed and recorded as required for the optimal treatment and follow up of the subject.
Study design:	A prospective, two-arm, unmasked, randomized, controlled study.
Objectives:	A prospective, randomized trial to evaluate and compare the clinical outcomes after implantation of the porous plate (polyethylene) with the silicone plate Ahmed Glaucoma Valve in subjects with intractable glaucoma.
Control Arm:	Subjects undergoing surgery with the silicone plate Ahmed Glaucoma Valve (Model FP7)
Treatment Arm:	Subjects undergoing surgery with the porous plate Ahmed Glaucoma Valve (Model M4)
Subject Population:	Patients with intractable glaucoma who are candidates for valve surgery.
Sample Size:	Total of 88 subjects with a planned 40 subjects in each arm. Each site can enroll a maximum of 40 subjects.
Follow-up duration:	12 months.

7. Study Population

This is a prospective, two-arm, unmasked, randomized, controlled study of 80 enrolled subjects with intractable glaucoma that have not responded to conventional medical and surgical therapy. The study will accrue up to 88 subjects to allow for a dropout rate of 10 %.

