All ophthalmic tests and examinations are for the selected study eye only.

If the subject satisfies all inclusion and exclusion criteria, the subject will be enrolled into the study.

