11.1 Sample Size Considerations

With a sample size of 40 in each group, the power of the study will be 0.8 (80%) to detect a 1.5 mmHg difference in intraocular pressure with a standard deviation of 3 mmHg. Investigators will screen and treat patients until the study is fully enrolled or the study is terminated. All subjects undergoing surgical intervention will be entered in the statistical analysis. Based on prior studies, failure to complete the 12 month post-operative period is not likely to exceed 10% of randomized subjects.

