11.4 Accrual

Maximum study accrual is estimated to be 88 subjects to accrue the targeted 80 subjects required to meet the study objectives. Maximum accrual allows for a 5% ineligibility rate and a 5% rate of coming off study before the planned surgical intervention. Once target accrual is reached, the study allows those within the screening process to be enrolled. As this allowance is not to exceed 4 patients, up to 84 patients may be treated with Ahmed Glaucoma Valves. Based upon accrual rates to prior drainage

implant studies, accrual is estimated at 15 per month; thus, accrual to the study should be completed in less than 6 months.

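### The 8-subject margin from 80 to 88 is given two purposes, and no stated allowance covers the post-operative loss of up to 10% that Section 11.1 foresees

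*Combined protocol and SAP*

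**What the plan says.** Four places bear on how many subjects reach the primary analysis.

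- **Section 6 (synopsis):** "Total of 88 subjects with a planned 40 subjects in each arm". It does not explain why the total exceeds twice 40.
- **Section 7:** the study is of 80 enrolled subjects, and "The study will accrue up to 88 subjects to allow for a dropout rate of 10" per cent.
- **Section 11.4:** "Maximum study accrual is estimated to be 88 subjects to accrue the targeted 80 subjects required to meet the study objectives". The margin is then explained: "Maximum accrual allows for a 5% ineligibility rate and a 5% rate of coming off study before the planned surgical intervention". Subjects already in screening when the target is met may still enter: "As this allowance is not to exceed 4 patients, up to 84 patients may be treated with Ahmed Glaucoma Valves".
- **Section 11.1:** power is computed for 40 per group, and "failure to complete the 12 month post-operative period is not likely to exceed 10% of randomized subjects".

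Sections 8.2 and 11 fix the order of events. Randomization is on the day of surgery, and the envelope is opened just before the local anesthetic. Section 5.1 sets the primary endpoint at 12 months.

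**The concern.** One margin of eight carries two labels. Section 7 calls it dropout. Section 11.4 assigns all of it to people found ineligible or lost before surgery, who are never randomized. The loss in 11.1 is expressed as a share of randomized subjects, so it comes later and affects different people. Eight subjects cannot cover both losses.

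These figures decide when accrual closes and how many month-12 pressures the primary comparison will have. A reader of Section 7 alone would think post-operative loss had been provided for; a reader of 11.4 would see that it had not. The plan does not say whether the 40 per group in 11.1 means operated subjects or subjects with a month-12 value, so the power statement may rest on a number that the accrual rules do not deliver at month 12.

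**Working it through.** **Inputs from the documents.** Target 80 and accrual 88 (Sections 6, 7, 11.4); pre-surgery losses 5% and 5% (11.4); treated maximum 84 (11.4); post-operative loss up to 10% of randomized subjects (11.1); difference 1.5 mmHg, SD 3 mmHg, 40 per group, 80% power (11.1); 1:1 allocation (Section 11).

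**Assumptions.** Two-sided alpha of 0.05 (the plan gives no alpha; 11.2 says two-tailed) and an independent two-sample t-test, because the arms are different people.

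**Step 1: reproduce the 88.**
- As a 10% addition: 80 × 1.10 = 88. By division: 80 / 0.90 = 88.9.
- As two successive 5% losses: 80 / 0.95² = 88.6.

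The figure fits either label to within one subject, but a single 10% loss uses it up.

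**Step 2: subjects operated.** 88 × 0.95 × 0.95 = 79.4, so 11.4 delivers about 80. Reaching 84 from 88 accrued requires total pre-surgery loss of no more than (88 − 84) / 88 = 4.5%, less than half of what 11.4 allows for. The 84 case is therefore the favourable end.

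**Step 3: subjects with a month-12 pressure at the 10% ceiling.**

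| Operated | × 0.90 | Per arm |
|---|---|---|
| 80 | 72.0 | 36.0 |
| 84 | 75.6 | 37.8 |

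With 84 operated, 80 completers remain only if the loss is at most 1 − 80/84 = 4.8%.

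**Step 4: what covering both losses would take.** 80 / 0.90 = 88.9, so 89 operated, above the maximum of 84. Adding the pre-surgery losses gives 80 / 0.90 / 0.95² = 98.5, so 99 accrued against 88.

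**Step 5: effect on power.** The standardized difference is 1.5 / 3 = 0.5. Power comes from the noncentral t distribution with noncentrality d√(n/2) and 2n − 2 degrees of freedom. The last column takes the stated 80% at 40 per arm as given, which corresponds to a detectable difference of 1.90 mmHg at SD 3 (d = 1.90/3 = 0.63).

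| Per arm | Power from 1.5 mmHg, SD 3 | Power if 80% held at 40 |
|---|---|---|
| 40 | 0.598 | 0.800 |
| 37.8 | 0.573 | 0.777 |
| 36 | 0.553 | 0.756 |

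On either basis the loss costs about 2 to 5 percentage points. The stated 80% does not reproduce from the plan's own inputs at 40 per arm. That is a separate and larger matter, but any restated power has to start from it.

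**The case against.** The best defence is that the sections can be read together. Section 7 speaks of 80 enrolled and 88 accrued; it never says that 80 remain at month 12. If dropout there is loose shorthand for loss between accrual and surgery, then 5% + 5% = 10%, and Sections 6, 7 and 11.4 describe one allowance. The maximum of 84 treated is also compatible with 88 accrued. This reading is fair and removes the conflict of wording. It does not remove the gap, because the plan then has no stated allowance for the post-operative loss named in 11.1.

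Two further defences carry less weight. All operated subjects enter the analysis (11.1, 11.6), and Section 8.5 asks subjects who withdraw to have the Month 12 assessments at an early visit. But the plan gives no method for a missing month-12 pressure and does not say that the early-withdrawal value stands in for it.

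A reader might infer several stronger things that the documents do not support:

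- **That the planned 80 are not delivered.** About 80 are operated; the shortfall is in month-12 completers, and the plan never says that the 80 are completers.
- **That 10% is the expected loss.** Section 11.1 gives it as a ceiling.
- **That nothing at all absorbs the loss.** The over-run to 84 would absorb up to 4.8%, although it is meant for people already in screening and is not guaranteed.
- **That a 5% ineligibility loss is impossible because Section 8.1 says "If the subject satisfies all inclusion and exclusion criteria, the subject will be enrolled into the study".** Section 11.4 speaks of accrual, not enrolment, so the two do not conflict.

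**Conclusion.** The point holds as a mismatch between the accrual allowance and the number behind the power statement. The margin of eight is labelled inconsistently, and on the precise account in 11.4 it is used up before randomization. At the 10% ceiling the month-12 comparison would have 72 to 76 subjects, 4 to 8 short of the 80 (two groups of 40) in 11.1. This rests on three conditions: 11.4 governs accrual, the loss reaches its ceiling, and a subject who does not complete contributes no month-12 value. A smaller loss shrinks the gap, and at 4.8% or less with 84 operated there is none. The effect on power is modest, so this is a correction the plan should make, not a fault that undermines the design.

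**What to change.** Reconcile the four sections without changing the number of patients.

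1. In Sections 6, 7 and 11.4, define 88 as the number accrued (screened), and 80, at most 84, as the number randomized and operated.
2. In Section 7, replace the dropout phrase with the two pre-surgery losses given in 11.4.
3. In 11.1, say whether 40 per group means operated or evaluable subjects. State that as few as 72 to 76 may have a month-12 pressure at the 10% ceiling, and restate power at 36 to 38 per arm with its alpha and test named.

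The cost is an edit to the wording and a less favourable stated evaluable number and power. Raising the operated target to cover the later loss is a different choice that would need more patients; this point does not require it.

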7.1 Inclusion Criteria

- Male or female of any race ≥ 18 years ≤ 80 years of age.
- Diagnosis of intractable glaucoma in the study eye, with the exception of silicone oil endotamponade induced glaucoma, which has not responded to conventional medical and surgical therapy.
- Elevated intraocular pressure > 21 mmHg in the study eye. Two consecutive measurements using Goldmann Applanation Tonometry will be obtained and the mean of those two measurements will be considered the subject's baseline intraocular pressure.
- Subject is a candidate for surgery in the study eye with a glaucoma drainage device.
- Subject is willing and able to sign the informed consent.

7.2 Exclusion Criteria

- Diagnosis of silicone oil endotamponade induced glaucoma in the study eye.
- History of prior drainage implant surgery in the study eye.
- History of cyclophotocoagulation of the study eye.
- Pregnancy.
- Prisoner.

Eligible subjects may have significant conjunctival scarring, precluding trabeculectomy in the study eye. Presence of diabetes mellitus, prior ocular surgery (with the exception of prior drainage implant surgery) or laser treatment for glaucoma, and use of glaucoma medications in the study eye will be noted, but are not exclusion criteria for determining eligibility.

8. Study Design

8.1 Screening Visit / Baseline Evaluation (Days -60 to -1)

After obtaining informed consent in the patient's, all potential subjects will undergo a baseline examination to determine study eligibility. Standard-of-care evaluations for glaucoma patients that are documented by the investigator may be utilized as the baseline evaluation to determine subject eligibility, provided the evaluations occur within 60 days prior to the planned surgical intervention, even if these evaluations occur prior to the subject consenting to participate in the study. This avoids the potentially unnecessary repetition of screening evaluations that are a part of the standard-of-care for glaucoma patients.

The following examinations, tests, and procedures are required as part of the baseline evaluation to determine subject eligibility and must be conducted within 60 days of the planned surgical intervention:

- Signing of the informed consent
- Review of Inclusion / Exclusion Criteria
- Demographic Information (Date of Birth, Sex, Self-Identified Ethnicity)
- Type of Glaucoma (Diagnosis)
- Review of Medical and Ocular Surgical History
- Review of Concomitant Systemic Medications
- Review of Concomitant Glaucoma Medications
- Review of History of Previous Glaucoma Treatments (laser and surgery)
- Review of Other Concomitant Ocular Medications
- Manifest Refraction and Snellen Visual Acuity
- Intraocular Pressure
 - Intraocular Pressure will be measured utilizing Goldmann applanation tonometry. Two consecutive measurements will be obtained and the mean of those two measurements will be considered the subject's baseline intraocular pressure. The intraocular pressure should be performed at the same time of day at all visits, when possible.
- Slit Lamp Examination
- Gonioscopy

- Funduscopy Examination
- 30-2 or 24-2 SITA Standard Humphrey Visual Field (if available, and may be used if obtained within 12 months of the planned surgical intervention)
- Determination of the study eye and subject eligibility (if both eyes qualify, the study eye will be the eye with the highest baseline intraocular pressure, then worst baseline visual acuity, then the right eye; unless in the investigator's best judgment the other eye should be selected)
- Urine or Serum Pregnancy Test for women of child-bearing potential (to be conducted as part of the site's standard pre-operative testing). The test must be negative to be eligible to participate.

All ophthalmic tests and examinations are for the selected study eye only.

If the subject satisfies all inclusion and exclusion criteria, the subject will be enrolled into the study.

8.2 Surgical Procedure (Day 0)

The surgical procedure must be performed within 60 days of the completion of the screening evaluation. The subject will be randomized to undergo surgical intervention with either the Model FP7, Silicone Plate Ahmed Glaucoma Valve (Group A) or the Model M4, Porous Plate Ahmed Glaucoma Valve (Group B), using the sealed envelope method of randomization. Randomization will take place on the day of surgery.

The following steps are considered guidelines for implantation of both the Model FP7 and Model M4. However, the use of any specific surgical technique or maneuver is at the sole discretion of the surgeon.

1. The implant should be examined and primed prior to implantation. Priming is accomplished by injecting 1cc balanced salt solution or sterile water through the drainage tube and valve, using a blunt 26 gauge cannula.

2. A fornix-based incision is made through the conjunctiva and Tenon's capsule. A pocket is formed at the superior quadrant between the medial or lateral rectus muscles by blunt dissection of Tenon's capsule from the episclera.
3. The valve body is inserted into the pocket between the rectus muscles and sutured to the episclera. The leading edge of the device should be at least 8-10mm from the limbus.
4. The drainage tube is trimmed to permit 2-3mm insertion of the tube into the anterior chamber. The tube should be bevel out to an anterior angle of 30° to facilitate insertion.
5. A paracentesis is performed and the anterior chamber is entered at the limbus with a sharp 23 gauge needle, parallel to the iris. Caution: Care must be taken to ensure that the drainage tube does not contact the iris or corneal endothelium after insertion.
6. The drainage tube is inserted into the anterior chamber approximately 2-3mm, through the needle track and parallel to the iris. The leading edge of the device should be 8-10mm from the limbus.
7. The exposed drainage tube is covered with a small piece of preserved, donor sclera or pericardium, which is sutured into place and the conjunctiva is closed. Note: As an alternative, a 2/3 thickness limbal-based scleral flap may be made. The tube is inserted into the anterior chamber through a 23 gauge needle puncture made under the flap. The flap is sutured closed.

8.3 Post-Operative Follow-Up Visits (1 Day; 7 Day; 1, 3, 6, 9, 12 months)

Follow-up visits will be conducted at the following post-operative time points:

- 1 Day Post-Operative (1 Day + 1 day)
- 7 Day Post-Operative (7 Days +/- 4 days)
- 1 Month Post-Operative (30 Days +/- 7 days)
- 3 Months Post-Operative (90 Days +/- 14 days)

- 6 Months Post-Operative (180 Days +/- 14 days)
- 9 Months Post-Operative (270 Days +/- 14 days)
- 12 Months Post-Operative (360 Days +/- 28 days)

The following examinations, tests, and procedures are required at each post-operative follow-up visit:

- Review of Adverse Events and Assessment of Device Complications
- Review of Concomitant Systemic Medications
- Review of Concomitant Glaucoma Medications
- Review of Other Concomitant Ocular Medications
- Snellen Visual Acuity and Manifest Refraction (per clarification in Administrative Letter #2 dated Oct 3, 2013, Manifest Refraction is optional).
- Intraocular Pressure
 - Intraocular Pressure will be measured utilizing Goldmann applanation tonometry. Two consecutive measurements will be obtained. The intraocular pressure should be performed at the same time of day at all visits, when possible.
- Slit Lamp Examination
- Gonioscopy (at Months 3, 6, 9, and 12 only)
- Funduscopy Examination
- Ultrasound biomicroscopy or Anterior Segment Optical Coherence Tomography to measure the capsule thickness around the plates (Months 6 and 12 only) (optional)

Post-Operative Follow-Up Visits (1 Day; 7 Day; 1, 3, 6, 9, 12 months)
All ophthalmic tests and examinations are for the selected study eye only.

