9.4 Device Explant, Repositioning, or Replacement

The device may be revised, repositioned, removed, or replaced by the same kind of device or another marked drainage device if the original device was damaged or determined to be not functioning. If surgical intervention for repositioning or replacement is required, the subject will be required at a minimum to complete all of the protocol required post-operative visits. If sequelae persist, the subject should be followed until all sequelae are considered to be stabilized or resolved.

10. Safety

At each visit, the ocular health of the subject will be assessed. The cornea, anterior chamber, trabecular meshwork, device implant location (if available), and fundus will be examined. Any ocular unanticipated adverse events occurring during the study whether they are considered to be device related or not, must be documented on the Adverse Event Case Report Form. Date and time of the event, event severity, treatment (if any), and the assessed relationship of the event to the study devices will be recorded on the Adverse Event Case Report Form. Conditions that exist at the time the subject is enrolled in the study do not need to be recorded on the Adverse Event Form as adverse events, unless they increase in severity during the study and constitute an unanticipated adverse event..

The collection and recording of unanticipated adverse events will begin at the start of the surgical intervention and will end at the subject's Month 12 or Early Termination Visit. Unanticipated adverse events must be followed until the adverse event has recovered or recovered with ongoing sequelae that will likely not change in the view of the investigator. This period *may* extend beyond study termination.

A brief overview of the differences between anticipated, unanticipated and serious adverse events is provided.

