10.1 Anticipated Adverse Events

Anticipated adverse events include those that might reasonably be expected to occur in this study because they are associated with glaucoma surgical procedures. Anticipated adverse events for both the porous plate and silicone plate glaucoma valves include:

- * Wound Leak
- * Shallow Anterior Chamber

- * Flat Anterior Chamber
- * Choroidal effusion
- * Exposure of Tube, Patch Graft, Plate
- * Severe Inflammation
- * Tube and/or Flow Obstruction
- * Corneal Edema
- * Motility Disturbance (i.e. Diplopia)
- * Suprachoroidal hemorrhage
- * Hypotony (≤ 5 mmHg)
- * Elevated intraocular pressure
- * Retinal Detachment

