10.5 Reporting Adverse Events

Identification and collection of anticipated and unanticipated adverse event information is the responsibility of the study investigator. All unanticipated adverse events should be documented by completing the Adverse Event Case Report Form. and submitted to the study coordinating site per study Manual of Procedures. All adverse events (**whether anticipated or unanticipated**) should be reported to the Institutional Review Board according to site guidelines.

The identification and collection of serious adverse events is the responsibility of the study investigator. All serious adverse events should be documented by completion of the Serious Adverse Event Case Report Form. All Serious Adverse events should be reported to the Medical Monitor within 24 hours of the site's notification of the event and to the Institutional Review Board according to site guidelines.

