10.7 Aggregate Review of Adverse Events

The Medical Monitor will be responsible for the continuous review of unanticipated adverse events.

11. Statistical Considerations

This prospective, two-arm, unmasked, randomized, controlled trial will evaluate and compare the clinical outcomes after implantation of the porous plate (polyethylene) Ahmed Glaucoma Valve (M4) with the silicone plate Ahmed Glaucoma Valve (FP7) in patients with intractable glaucoma. Subjects will be randomized in a 1:1 ratio to one of two surgical intervention arms - surgical intervention with the Model FP7, Silicone Plate Ahmed Glaucoma Valve (Group A) or the Model M4, Porous Plate Ahmed Glaucoma Valve (Group B). The computer-generated randomization scheme (using varying block sizes of 2 to 4) will be completed by a staff member of the University of Virginia, Department of Ophthalmology, whose sole role in this study is to generate the randomization scheme. The subject surgical intervention arm assignment will be placed in a sealed envelope, securely delivered to the sites, and will be accessed by the site study staff in the site Surgical Admission Suite immediately prior to local anesthesia injection for the surgical procedure. Post-randomization, the assigned surgical intervention arm will be unmasked to the subject.

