11.3 Assessment of the Secondary Endpoints

This secondary endpoint is the mean number of anti-glaucoma medications and surgical success in the porous plate group as compared to the silicone plate group at 12 months. The baseline number of medications will be compared to check for statistically significant differences and, if needed, a change from baseline analysis will be performed. The statistical significance of the differences in the number of medications will be determined using two-tailed paired t-tests. The mean number of medications at individual time points will be compared in the two groups. Kaplan-Meier survival analysis will be performed for statistical analysis of success rates, with comparisons of groups using the log rank test. Complications will be compared using comparison of proportions (z) test.

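### Motility disturbance (diplopia) falls within the complications compared between plates, but the plan sets no standard way to ascertain it and records no baseline status

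*Combined protocol and SAP*

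**What the plan says.** - **Listed event.** Section 10.1 includes "Motility Disturbance (i.e. Diplopia" among the events anticipated with both the porous and the silicone plate.
- **Comparison.** Section 11.3 ends with "Complications will be compared using comparison of proportions (z) test". It does not say which complications are meant.
- **Named tests.** Section 8.1 (baseline), Section 8.3 (follow-up) and the schedule in 8.6 name acuity and refraction, tonometry, slit lamp, gonioscopy, funduscopy, a screening visual field and optional capsule imaging. Section 10 describes the safety examination at each visit: "The cornea, anterior chamber, trabecular meshwork, device implant location (if available), and fundus will be examined". Eye movement, alignment and double vision appear in none of these.
- **Study-eye rule.** Sections 8.1 and 8.3 both close with it: "All ophthalmic tests and examinations are for the selected study eye only".
- **General review.** Section 8.3 requires "Review of Adverse Events and Assessment of Device Complications" at each of the seven scheduled post-operative visits. Section 10.5 adds: "Identification and collection of anticipated and unanticipated adverse event information is the responsibility of the study investigator".
- **Recording.** Section 10.5 states: "All unanticipated adverse events should be documented by completing the Adverse Event Case Report Form". Section 10 uses the same restriction. Diplopia is an anticipated event.
- **Masking.** The opening of Section 11 says that after randomization "the assigned surgical intervention arm will be unmasked to the subject".
- **Prior surgery.** Section 7.2 allows earlier ocular surgery other than a drainage implant.

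**The concern.** Several listed complications, such as a flat chamber, corneal edema, choroidal effusion or hypotony, have a required examination that can show them. Motility disturbance has none. Whether a case is found depends on what each investigator does within a general review, and that can differ between sites and between arms.

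Three things could distort the compared proportions:

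- **Under-counting.** Cases missed equally in both arms shrink the observed difference and cost power.
- **Unequal capture.** Subjects and staff know the plate. If one arm is asked more often or reports more readily, a difference can appear where none exists.
- **Mixing with earlier diplopia.** Prior ocular surgery is allowed and no baseline status is recorded, so new and pre-existing diplopia cannot be reliably told apart.

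A real difference is plausible on the plan's own description. Section 2 says the porous material allows tissue to grow in, and Section 8.2 places the plate between rectus muscles. Analysts cannot recover this information after the trial.

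**Working it through.** **Stated figure.** There is none to reproduce. The documents give no expected rate, capture rate or power for any complication.

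**Text check.**

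| Question | Where | Finding |
|---|---|---|
| Is the event listed? | 10.1 | Yes, for both plates |
| Is it compared? | 11.3 | By natural reading; the complications are not enumerated |
| Does a named test target it? | 8.1, 8.3, 8.6, 10 | No |
| Is baseline status recorded? | 8.1 | General and ocular surgical history only |
| Is there a route for capture? | 8.3, 10.5 | Yes, a required review, method unspecified |
| Is there a named form? | 10, 10.5 | Only for unanticipated or serious events |

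**Illustration of size.** From the documents: n = 40 per arm (11.1), 1:1 allocation (11), z test of proportions (11.3). Assumed: two-sided level 0.05, all true rates, all capture rates.

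Observed rate = true rate × capture. With x and y events in the two arms and p = (x + y)/80,

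z = (x/40 − y/40) / √[p(1 − p)(2/40)], significant if |z| ≥ 1.96.

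Example at expected counts for true rates of 25% v 5%:

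- Full capture gives 10 v 2 events. p = 12/80 = 0.15, standard error = √(0.15 × 0.85 × 0.05) = 0.080, z = 0.20/0.080 = 2.50.
- 50% capture gives 5 v 1 events. p = 6/80 = 0.075, standard error = √(0.075 × 0.925 × 0.05) = 0.059, z = 0.10/0.059 = 1.70.

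The probabilities below come from summing the two binomial distributions exactly over all (x, y).

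Power with equal capture in both arms:

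| True rates | 100% | 75% | 50% | 25% |
|---|---|---|---|---|
| 25% v 5% | 0.76 | 0.63 | 0.44 | 0.16 |
| 20% v 5% | 0.57 | 0.45 | 0.30 | 0.09 |

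With full capture, 15% v 5% gives only 0.35 and 10% v 5% only 0.15.

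A normal approximation gives slightly different values (0.53 for 20% v 5% at full capture, 0.28 at 50%) and the same pattern.

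False-positive rate with equal true rates:

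| True rate, both arms | Full capture | 75% v 50% | 80% v 40% |
|---|---|---|---|
| 20% | 0.05 | 0.11 | 0.21 |
| 10% | 0.06 | 0.08 | 0.12 |
| 5% | 0.04 | 0.03 | 0.04 |

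**The case against.** A reader might infer that diplopia cannot be detected at all and that only volunteered complaints will count. The documents do not support that. The review in Section 8.3 is a required procedure at every post-operative visit, and Section 10.5 makes investigators responsible for identifying anticipated events. They may ask about double vision or check movement of the study eye. An unspecified method is not the same as spontaneous reporting.

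A reader might also infer that the study-eye rule forbids the assessment. Read literally, it excludes a two-eye alignment or diplopia test. It governs tests and examinations, so it bars neither a question nor a check of the study eye.

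Nor does the wording in Section 10.1 show that restricted movement without double vision would be discarded. The listed item is motility disturbance, and nothing says how such a case is scored.

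Other objections stand in part:

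- The baseline review of ocular surgical history may reveal some earlier motility problems. It is not a record of diplopia status.
- The Manual of Procedures, which is not among the documents, may specify the review or a form for anticipated events.
- Every rate in the illustration is assumed. At low true rates the comparison says little even with perfect capture, and at 5% unequal capture does not inflate the false-positive rate.
- Complication comparison is not an endpoint in Section 5.1 or 5.2.

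These points limit the severity. They do not supply a standard question or a baseline.

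**Conclusion.** The point holds as a minor one: ascertainment of motility disturbance is unstandardised and lacks a baseline in an unmasked trial, so the proportions entering the Section 11.3 comparison may be too low, unequally captured, or mixed with earlier diplopia. Including this event in that comparison is an inference, though a natural one.

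The size cannot be derived from the documents. On the assumptions shown, halving capture could take power for a large difference (25% v 5%) from 0.76 to 0.44. Capture of 75% v 50% could roughly double the false-positive rate if the true rate is 20% in both arms, with little effect at 10% and none at 5%. Neither under-counting nor bias between arms is shown to have occurred; the plan leaves room for both.

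**What to change.** 1. In Sections 8.1, 8.3 and 8.6, add one yes/no question on double vision, worded identically for every subject, at baseline and within the existing adverse event review at each post-operative visit.
2. Record the answer on a study form for every subject, and name that form. Sections 10 and 10.5 send only unanticipated events to the Adverse Event form.
3. State that the study-eye rule does not apply to this question.
4. In Section 11.3, compare new or worsened diplopia relative to baseline.

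The cost is one form item at eight time points (baseline plus seven visits), a slightly longer visit and a sentence in 11.3. Reported diplopia rates will probably be higher than without a fixed question. No equipment is needed.

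A scripted question equalises prompting. It does not remove reporting bias from knowledge of the plate, and it will not find restricted movement without double vision. An added eye-movement examination is not needed for this point. A subgroup defined by vision in both eyes is not proposed either, because fellow-eye acuity is not collected.
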